4.4.2. Secondary Endpoints and Analysis Methodology

The secondary endpoints at Week 12 in Period 2 include:

- Proportion of participants achieving:
 - o ACR50
 - o ACR70
 - o Remission or LDA in terms of DAS28-hsCRP
 - o Remission or LDA in terms of DAS28-ESR
 - o Remission or LDA in terms of SDAI, and
 - o Remission or LDA in terms of CDAI
- Mean change from baseline in:
 - o DAS28-hsCRP
 - o SDAI
 - CDAI
 - o TJC68
 - o SJC66, and
 - o Physician's Global Assessment of Disease Activity (VAS)
 - o Patient's Global Assessment of Disease Activity (VAS)
 - o Patient's Assessment of Arthritis Pain (VAS), and
 - o patient's assessment of physical function using HAQ-DI
 - Duration of morning joint stiffness
 - Severity of morning joint stiffness
 - FACIT-F scores
 - o Short Form-36 health survey acute form (SF-36) domains
 - o SF-36 Physical Component Summary, and
 - o SF-36 Mental Component Summary.

The secondary endpoints at Week 24 and Week 60 in Period 3 include:

- Proportion of participants achieving:
 - o ACR20
 - o ACR50
 - o ACR70
 - o Remission or LDA in terms of DAS28-hsCRP
 - o Remission or LDA in terms of DAS28-ESR
 - o Remission or LDA in terms of SDAI, and
 - o Remission or LDA in terms of CDAI
- Mean change from baseline in:
 - o DAS28-hsCRP
 - o SDAI
 - o CDAI
 - o TJC68
 - o SJC66, and
 - o Physician's Global Assessment of Disease Activity (VAS).

4.4.2.1. Main Analytical Approach

4.4.2.1.1. ACR50 and ACR70

ACR50 and ACR70 are calculated in the same manner as ACR20 but are based on 50% and 70% improvement, respectively.

Summaries and analyses similar to those described for ACR20 in Section 4.4.1 will be conducted for ACR50 and ACR70. Any missing data (for example, missing due to missing a visit) will be imputed using NRI.

4.4.2.1.2. DAS28-hsCRP

The change from baseline of DAS28-hsCRP at Week 12 for the peresolimab treatment group will be compared with placebo.

An MMRM model, as described in Section 4.1, will be used to test the treatment difference of each peresolimab treatment group versus placebo. A hypothetical strategy will be used to handle intercurrent events. Any missing data (for example, missing due to missing a visit) will not be imputed.

4.4.2.1.3. SDAI

The change from baseline of SDAI at Week 12 for the peresolimab treatment group will be compared with placebo.

A MMRM model, as described in Section 4.1, will be used to test the treatment difference of each peresolimab treatment group versus placebo. A hypothetical strategy will be used to handle intercurrent events. Any missing data (for example, missing due to missing a visit) will not be imputed.

4.4.2.1.4. CDAI

The change from baseline of CDAI at Week 12 for the peresolimab treatment group will be compared with placebo.

A MMRM model, as described in Section 4.1, will be used to test the treatment difference of each peresolimab treatment group versus placebo. A hypothetical strategy will be used to handle intercurrent events. Any missing data (for example, missing due to missing a visit) will not be imputed.

4.4.2.1.5. ACR Core Set Values

The change from baseline of the following individual components at Week 12 of the ACR core set will be compared with placebo:

- TJC (68 joint count; 0 to 68)
- SJC (66 joint count; 0 to 68)
- Patient's Assessment of Pain (VAS; 0 to 100 mm)
- Patient's Global Assessment of Disease Activity (VAS; 0 to 100 mm)
- Physician's Global Assessment of Disease Activity (VAS; 0 to 100 mm)
- Patient's Assessment of Physical Function as measured by the HAQ-DI (0 to 3 by 0.125)
- Acute Phase reactant as measured by hsCRP (mg/dL)

A MMRM model, as described in Section 4.1, will be used to test the treatment difference of each peresolimab treatment group versus placebo. A hypothetical strategy will be used to handle intercurrent events. Any missing data (for example, missing due to missing a visit) will not be imputed.

4.4.2.1.6. DAS28-hsCRP Remission and Low Disease Activity

DAS28-hsCRP remission and LDA at Week 12 for the peresolimab treatment group will be compared with placebo.

A logistic regression model will be used, as described in Section 4.1, to test the treatment difference of each peresolimab treatment group versus placebo. A composite strategy will be used to handle for intercurrent events. Any missing data (for example, missing due to missing a visit) will be imputed using NRI.

4.4.2.1.7. DAS28-ESR Remission and Low Disease Activity

DAS28-ESR remission and LDA at Week 12 for the peresolimab treatment group will be compared with placebo.

A logistic regression model will be used, as described in Section 4.1, to test the treatment difference of each peresolimab treatment group versus placebo. A composite strategy will be used to handle intercurrent events. Any missing data (for example, missing due to missing a visit) will be imputed using NRI.

4.4.2.1.8. SDAI Remission and Low Disease Activity

SDAI remission and LDA at Week 12 for the peresolimab treatment group will be compared with placebo.

A logistic regression model will be used, as described in Section 4.1, to test the treatment difference of each peresolimab treatment group versus placebo. A composite strategy will be used to handle intercurrent events. Any missing data (for example, missing due to missing a visit) will be imputed using NRI.

4.4.2.1.9. CDAI Remission and Low Disease Activity

CDAI remission and LDA at Week 12 for the peresolimab treatment group will be compared with placebo.

A logistic regression model will be used, as described in Section 4.1, to test the treatment difference of each peresolimab treatment group versus placebo. A composite strategy will be used to handle intercurrent events. Any missing data (for example, missing due to missing a visit) will be imputed using NRI.

4.4.2.1.10. Duration and Severity of Morning Joint Stiffness

The change from baseline of the duration and severity of morning joint stiffness at Week 12 for the peresolimab treatment group will be compared with placebo.

A MMRM model, as described in Section 4.1, will be used to test the treatment difference of each peresolimab treatment group versus placebo. A hypothetical strategy will be used to handle intercurrent events. Any missing data (for example, missing due to missing a visit) will not be imputed.

4.4.2.1.11. FACIT-F

The change from baseline of FACIT-F at Week 12 for the peresolimab treatment group will be compared with placebo.

A MMRM model, as described in Section 4.1, will be used to test the treatment difference of each peresolimab treatment group versus placebo. A hypothetical strategy will be used to handle intercurrent events. Any missing data (for example, missing due to missing a visit) will not be imputed.

4.4.2.1.12. SF-36 Domain and Component Summary

The change from baseline of Short Form-36 version 2 health survey acute form (SF-36v2) acute for the peresolimab treatment group will be compared with placebo.

An ANCOVA model, as described in Section 4.1, will be used to test the treatment difference of each peresolimab treatment group versus placebo. A hypothetical strategy will be used to handle intercurrent events. Any missing data (for example, missing due to missing a visit) will be imputed using LOCF.

4.4.3. Supportive Secondary Endpoints

4.4.3.1. Definition of Endpoints

The supportive secondary endpoints include:

- Proportion of participants achieving LDA or remission at Weeks 24 and 60 for
 - o DAS28-hsCRP

- o DAS28-ESR
- o SDAI, and
- o CDAI
- Proportion of participants achieving ACR20, ACR50, or ACR70 at Weeks 24 and 60
- Change from baseline at Weeks 24 and 60 for ACR core set values
 - o TJC68
 - o SJC66, and
 - o Physician's Global Assessment of Disease Activity (VAS)
- Change from baseline at Weeks 24 and 60 for mean
 - o DAS28-hsCRP
 - o SDAI, and
 - o CDAI
- Observed trough drug concentration at Week 12

4.4.3.2. Main Analytic Approach

For continuous endpoints, summary tables at assessed time points and the change from the baseline assessment will be presented by treatment groups. Observed mean, standard deviation, minimum, median, and maximum will be reported. A hypothetical strategy will be used to handle intercurrent events. Any missing data (for example, missing due to missing a visit) will be imputed with LOCF.

For dichotomous endpoints, summary tables at assessed time points will be presented by treatment groups. The number of observed responses, the rate of observed response, and 95% CI will be reported. A composite strategy will be used to handle intercurrent events. Any missing data (for example, missing due to missing a visit) will be inputted using NRI.

4.5. Exploratory Endpoints Analysis

Table KDAF.4.1. Description and Derivation of Efficacy and Patient Reported Outcome Measures

Measure	Description	Variable	Derivation/Comment	Definition of Missing
American College of Rheumatology (ACR)	ACR score is a composite of clinical, laboratory, and functional measures in RA to assess relief of signs and symptoms.	ACR20/50/70	See Appendix 6 (Section 6.6) for details.	See Appendix 6 (Section 6.6) for details.
Disease Activity Score – high- sensitivity C-reactive	Disease Activity The DAS28-CRP is a measure of disease activity in 28 joints that consists of a	DAS28-hsCRP	DAS28-hsCRP = $0.56\sqrt{\text{TJC28}}$ + $0.28\sqrt{\text{SJC28}}$ + $0.36\ln(\text{hsCRP}$ + $1)$ + 0.014PatGA + 0.96	If 1 or more variables are missing, then set to missing.
(DAS28-hsCRP) sensitivity C-reactive pr (measured in mg/L), and	following variables: TJC, SJC, high- sensitivity C-reactive protein (hsCRP) (measured in mg/L), and Patient's Global	Change from baseline in DAS28-hsCRP	Calculated as: Observed DAS28-hsCRP score – baseline DAS28-hsCRP	Missing if baseline or observed value are missing.
	Assessment of Disease Activity (PatGA) recorded by patients on a 0- to 100-mm VAS. For DAS28-hsCRP, the 28 joints to	DAS28-hsCRP Remission DAS28-hsCRP Low	Remission is defined as observed DAS28-hsCRP score of <2.6. DAS28-hsCRP LDA is defined as	Missing if observed is missing. Missing if observed is
be examined and assessed as tender or not tender for TJC (TJC 28) and as swollen or not swollen for SJC (SJC 28) are a subset of those assessed for the TJC and SJC and include 14 joints on each side of the patient's body: the 2 shoulders, the 2 elbows, the 2 wrists, the 10 metacarpophalangeal joints, the 2 interphalangeal joints of the thumb, the 8 proximal interphalangeal joints, and the 2 knees. (Vander Cruyssen et al. 2005)	Disease Activity (LDA)	observed DAS28-hsCRP score of ≤3.2.	missing.	
Disease Activity Score – erythrocyte sedimentation rate	Similar to DAS28-hsCRP, except erythrocyte sedimentation rate (ESR) is used in replacement of hsCRP.	DAS28-ESR	DAS28-ESR = $0.56\sqrt{\text{TJC28}}$ + $0.28\sqrt{\text{SJC28}}$ + $0.36\ln(\text{ESR} + 1)$ + 0.014PatGA + 0.96	If 1 or more variables are missing, then set to missing.
(DAS28-ESR)		Change from baseline in DAS28-ESR	Calculated as: Observed DAS28-ESR score – baseline DAS28-ESR	Missing if baseline or observed value are missing.

		TJC68	TJC68)/baseline TJC68	missing.
Tender Joint Count –	The number of tender and painful joints will	TJC28 score	TJC28 is calculated as: rounding up	If more than half of
28 joint counts	be determined by examination of 28 joints		(number of tender joints)/(number	the individual joint
(TJC28)	(14 joints on each side of the patient's		of evaluable joints)×28	scores are
	body). The 28 joints to be assessed and		See Appendix 7 (Section 6.7) for	nonevaluable, total
	classified as tender or not tender.		details.	score missing.
		Change from baseline	Calculated as: Observed TJC28 –	Missing if baseline or
		in TJC28	baseline TJC28	observed value are
				missing.
		Percent improvement	Calculated as:	Missing if baseline or
		from baseline in	100 × (baseline TJC28 – observed	observed value are
		TJC28	TJC28)/baseline TJC28	missing.
Swollen Joint Count	The number of swollen joints will be	SJC66 score	SJC66 is calculated as: rounding up	If more than half of
– 66 joint counts	determined by examination of 66 joints		(number of swollen joints)/(number	the individual joint
(SJC66)	(33 joints on each side of the patient's		of evaluable joints)×66	scores are
	body). The 66 joints to be assessed and		See Appendix 7 (Section 6.7) for	nonevaluable, total
	classified as swollen or not swollen.		details.	score missing.
		Change from baseline	Calculated as: Observed SJC66 –	Missing if baseline or
		in SJC66	baseline SJC66	observed value are
				missing.
		Percent improvement	Calculated as:	Missing if baseline or
		from baseline in	100 × (baseline SJC66 – observed	observed value are
		SJC66	SJC66)/baseline SJC66	missing.
Swollen Joint Count	The number of swollen joints will be	SJC28 score	SJC 28 is calculated as: rounding up	If more than half of
– 28 joint counts	determined by examination of 28 joints		(number of swollen joints)/(number	the individual joint
(SJC28)	(14 joints on each side of the patient's		of evaluable joints)×28	scores are
	body). The 28 joints to be assessed and		See Appendix 7 (Section 6.7) for	nonevaluable, total
	classified as swollen or not swollen.		details.	score missing.
		Change from baseline	Calculated as: Observed SJC28 –	Missing if baseline or
		in SJC28	baseline SJC28	observed value are
				missing.

Measure	Description	Variable	Derivation/Comment	Definition of Missing
		Percent improvement	Calculated as:	Missing if baseline or
		from baseline in	100 × (baseline SJC28 – observed	observed value are
		SJC28	SJC28)/baseline SJC28	missing.
Physician's Global	Overall assessment of the severity of the	PGA VAS score	No derivation; ranges from 0 to	Missing if observed
Assessment of	patient's current RA activity using a		100 mm, where 0 represents no	value is missing.
Disease Activity	100-mm horizontal VAS. The investigator		disease activity and 100 represents	
(PGA) Visual Analog	making the assessment must be a		extremely active disease activity.	
Scale (VAS)	rheumatologist or medically qualified	Change from baseline	Calculated as: Observed PGA –	Missing if baseline or
	physician	in PGA VAS	baseline PGA	observed value are
				missing.
		Percent improvement	Calculated as:	Missing if baseline or
		from baseline in PGA	100 × (baseline PGA – observed	observed value are
		VAS	PGA)/baseline PGA	missing.
PatGA VAS	Assesses the patient's overall assessment of	PatGA VAS score	No derivation; ranges from 0 to	Missing if observed
	his or her RA activity by marking a		100 mm, where 0 represents no	value is missing.
	100-mm horizontal VAS. (Nikiphorou et al.		disease activity and 100 represents	
	2016)		extremely active disease activity.	
		Change from baseline	Calculated as: Observed PatGA –	Missing if baseline or
		in PatGA VAS	baseline PatGA	observed value are
				missing.
		Percent improvement	Calculated as:	Missing if baseline or
		from baseline in	100 × (baseline PatGA – observed	observed value are
		PatGA VAS	PatGA)/baseline PatGA	missing.
Patient's Assessment	Assesses the patient's current level of joint	Pain VAS score	No derivation; ranges from 0 to	Missing if observed
of Arthritis Pain	pain by marking a vertical tick on a		100 mm, where 0 represents no joint	value is missing.
(Pain) VAS	100-mm horizontal VAS.		pain and 100 represents the worse	
			joint pain.	
		Change from baseline	Calculated as: Observed Pain –	Missing if baseline or
		in Pain VAS	baseline Pain	observed value are
				missing.
		Percent improvement	Calculated as:	Missing if baseline or
		from baseline in Pain	100 × (baseline Pain – observed	observed value are
		VAS	Pain)/baseline Pain	missing.

Measure	Description	Variable	Derivation/Comment	Definition of Missing
Patient's Assessment of Physical Function Health Assessment Questionnaire – Disability Index (HAQ-DI)	Patient-reported standardized questionnaire that is commonly used in RA to measure disease-associated disability (assessment of physical function). It consists of 24 questions referring to 8 domains: dressing/grooming, arising, eating, walking, hygiene, reach, grip, and other daily	HAQ-DI score	Sum of the highest subcategory scores within 8 categories and adjust for aids/devices and/or help from another person. It ranges from 0 to 3 by 0.125. See Appendix 7 (Section 6.7) for details.	Missing if <6 categories completed.
	activities. (Fries et al. 1980, 1982; Fries 1983; Ramey et al. 1996)	Change from baseline in HAQ-DI	Calculated as: Observed HAQ-DI – baseline HAQ-DI	Missing if baseline or observed value are missing.
		Percent improvement from baseline in HAQ-DI	Calculated as: 100 × (baseline HAQ-DI – observed HAQ-DI)/baseline HAQ-DI	Missing if baseline or observed value are missing.
		HAQ-DI Minimal Clinically Important Difference (MCID)	MCID is defined as baseline HAQ-DI – observed HAQ-DI ≥0.22 Note: participants with HAQ-DI score <0.22 at baseline will be excluded from the analysis set. Additional threshold may be considered if necessary.	Missing if baseline or observed value are missing.
hsCRP (mg/dL)	The ACR core set measure and DAS28-hsCRP core set measure of acute	hsCRP	No derivation as raw laboratory result	Missing if missing.
	phase reactant. Assayed by Lilly-designated laboratory.	Change from baseline in hsCRP	Calculated as: Observed hsCRP – baseline hsCRP	Missing if baseline or observed value are missing.
		Percent improvement from baseline in hsCRP	Calculated as: 100 × (baseline hsCRP – observed hsCRP)/baseline hsCRP	Missing if baseline or observed value are missing.
ESR (mm/h)	Laboratory measure in DAS28-ESR. Assayed and evaluated locally.	ESR	No derivation as raw laboratory result	Missing if missing.
		Change from baseline in ESR	Calculated as: Observed ESR – baseline ESR	Missing if baseline or observed value are missing.

Measure	Description	Variable	Derivation/Comment	Definition of Missing
		Percent improvement	Calculated as:	Missing if baseline or
		from baseline in ESR	100 × (baseline ESR – observed	observed value are
			ESR)/baseline ESR	missing.
Duration and severity	The duration of morning joint stiffness is a	Duration of morning	No derivation	Missing if missing.
of Morning Joint	patient-administered item that allows for the	joint stiffness		
Stiffness	patients to enter the length of time in	Change from baseline	Calculated as: Observed duration –	Missing if baseline or
	minutes that their morning joint stiffness	in duration of	baseline duration	observed value are
	lasted on the day prior to that visit using an	morning joint		missing.
	electronic patient-reported outcomes	stiffness		
	(ePRO) tablet. Durations recorded as longer	Severity of morning	No derivation	Missing if missing.
	than 12 hours (720 minutes) will be	joint stiffness		
	truncated to 720 minutes for analysis.	Change from baseline	Calculated as: Observed duration –	Missing if baseline or
	The severity of morning joint stiffness is a	in severity of	baseline duration	observed value are
	single item, 11-point horizontal scale that	morning joint		missing.
	captures the severity of morning joint	stiffness		
	stiffness using a scale from 0 to 10, where 0			
	implies no joint stiffness, and 10 implies			
	joint stiffness as bad as you can imagine.			
	The worst level of joint stiffness in the last			
	7 days will be used for analysis.			
Functional	The FACIT-F scale (Cella and Webster	FACIT-F score	Sum of 13 symptom-specific items.	Missing if >6 items
Assessment of	1997) is a brief, 13-item, symptom-specific		It ranges from 0 to 52 with 0 being	are missing.
Chronic Illness	questionnaire that specifically assesses the		the worst possible score.	
Therapy – Fatigue	self-reported severity of fatigue and its		See Appendix 7 (Section 6.7) for	
(FACIT-F)	impact upon daily activities and		details.	
	functioning. The FACIT-F uses 0 ("not at	Change from baseline	Calculated as: Observed FACIT-F –	Missing if baseline or
	all") to 4 ("very much") numeric rating	in FACIT-F	baseline FACIT-F	observed value are
	scales to assess fatigue and its impact in the			missing.
	past 7 days. Scores range from 0 to 52 with			
	higher scores indicating less fatigue. (Cella			
	1997)			
		8 associated domain	Refer to the manual "How to Score	To be added.
		scores:	Version 2 of the SF-36 Health	
			Survey" (Ware et al. 2000)	

Measure	Description	Variable	Derivation/Comment	Definition of Missing
Short Form-36 version 2 health survey acute form (SF-36v2)	The SF-36v2 Acute measure is a subjective, generic, health-related quality of life instrument that is patient-reported and consists of 36 questions covering 8 health domains: physical functioning, bodily pain, role limitations due to physical problems, role limitations due to emotional problems, general health perceptions, mental health, social function, and vitality. Each domain is scored by summing the individual items and transforming the scores into a 0 to 100 scale with higher scores indicating better health status or functioning. In addition, 2 summary scores, the physical component	 Physical Functioning Role Physical Bodily Pain General Health Vitality Social Functioning Role Emotional Mental Health 2 component Scores: MCS Score PCS Score 		
	score (PCS) and the mental component score (MCS), will be evaluated based on the 8 SF-36v2 Acute domains (McHorney et al. 1993; Ware et al. 2007; Ware and Sherbourne 1992; Maruish 2011).	Change from baseline in 8 associated domain scores and 2 component scores	Calculated as: Observed value – baseline value	Missing if baseline or observed value are missing.

Abbreviations: PGA = physician's global assessment; PatGA = patient's global assessment; RA = rheumatoid arthritis; SF-36 = Short Form-36 health survey acute form; SJC = swollen joint count; TJC = tender joint count.

Table KDAF.4.2. Description of Efficacy and Patient Reported Outcome Analyses

Measure	Variable	Estimand	Analysis Method	Population	Comparison and Timepoint	Analysis Type
American College of Rheumatology (ACR)	ACR20	Composite	Logistic with NRI	mITT	PER100Q4W vs. PBO; PER400Q4W vs. PBO; PER1000Q4W vs. PBO; At Week 12 and all other scheduled visits in Period 2	Primary analysis is at Week 12.
		Composite	Descriptive statistics with NRI	Maintenance	No between-treatment comparison; At Week 24 and all other scheduled visits in Period 3A	Secondary analysis is at Week 24.
		Composite	Descriptive statistics with NRI	Maintenance Primary; Maintenance Secondary; Maintenance Tertiary	No between-treatment comparison; At Week 60 and all other scheduled visits in Period 3B	Secondary analysis is at Week 60.
	ACR50/70	Composite	Logistic with NRI	mITT	PER100Q4W vs. PBO; PER400Q4W vs. PBO; PER1000Q4W vs. PBO; At Week 12 and all other scheduled visits in Period 2	Secondary analysis is at Week 12.
		Composite	Descriptive statistics with NRI	Maintenance	No between-treatment comparison; At Week 24 and all other scheduled visits in Period 3A	Secondary analysis is at Week 24.
		Composite	Descriptive statistics with NRI	Maintenance Primary; Maintenance Secondary; Maintenance Tertiary	No between-treatment comparison; At Week 60 and all other scheduled visits in Period 3B	Secondary analysis is at Week 60.

Measure	Variable	Estimand	Analysis Method	Population	Comparison and Timepoint	Analysis Type
DAS28-hsCRP	Change from baseline (and/or percent improvement from baseline)	Hypothetical	MMRM with no missing data imputation	mITT	PER100Q4W vs. PBO; PER400Q4W vs. PBO; PER1000Q4W vs. PBO; At Week 12 and all other scheduled visits in Period 2	Secondary analysis is at Week 12.
		Hypothetical	Descriptive statistics with LOCF	Maintenance	No between-treatment comparison; At Week 24 and all other scheduled visits in Period 3A	Secondary analysis is at Week 24.
		Hypothetical	Descriptive statistics with LOCF	Maintenance Primary; Maintenance Secondary; Maintenance Tertiary	No between-treatment comparison; At Week 60 and all other scheduled visits in Period 3B	Secondary analysis is at Week 60.
	LDA; Remission	Composite	Logistic with NRI	mITT	PER100Q4W vs. PBO; PER400Q4W vs. PBO; PER1000Q4W vs. PBO; At Week 12 and all other scheduled visits in Period 2	Secondary analysis is at Week 12.
		Composite	Descriptive statistics with NRI	Maintenance	No between-treatment comparison; At Week 24 and all other scheduled visits in Period 3A	Secondary analysis is at Week 24.
		Composite	Descriptive statistics with NRI	Maintenance Primary; Maintenance Secondary; Maintenance Tertiary	No between-treatment comparison; At Week 60 and all other scheduled visits in Period 3B	Secondary analysis is at Week 60.

Measure	Variable	Estimand	Analysis Method	Population	Comparison and Timepoint	Analysis Type
DAS28-ESR	LDA; Remission	Composite	Logistic with NRI	mITT	PER100Q4W vs. PBO; PER400Q4W vs. PBO; PER1000Q4W vs. PBO; At Week 12 and all other scheduled visits in Period 2	Secondary analysis is at Week 12.
		Composite	Descriptive statistics with NRI	Maintenance	No between-treatment comparison; At Week 24 and all other scheduled visits in Period 3A	Secondary analysis is at Week 24.
		Composite	Descriptive statistics with NRI	Maintenance Primary; Maintenance Secondary; Maintenance Tertiary	No between-treatment comparison; At Week 60 and all other scheduled visits in Period 3B	Secondary analysis is at Week 60.

[figure not shown]
Measure	Variable	Estimand	Analysis Method	Population	Comparison and Timepoint	Analysis Type
SDAI; CDAI	Change from baseline (and/or percent improvement from baseline)	Hypothetical	MMRM with no missing data imputation	mITT	PER100Q4W vs. PBO; PER400Q4W vs. PBO; PER1000Q4W vs. PBO; At Week 12 and all other scheduled visits in Period 2	Secondary analysis is at Week 12.
		Hypothetical	Descriptive statistics with LOCF	Maintenance	No between-treatment comparison; At Week 24 and all other scheduled visits in Period 3A	Secondary analysis is at Week 24.
		Hypothetical	Descriptive statistics with LOCF	Maintenance Primary; Maintenance Secondary; Maintenance Tertiary	No between-treatment comparison; At Week 60 and all other scheduled visits in Period 3B	Secondary analysis is at Week 60.

Measure	Variable	Estimand	Analysis Method	Population	Comparison and Timepoint	Analysis Type
	LDA; Remission	Composite	Logistic with NRI	mITT	PER100Q4W vs. PBO; PER400Q4W vs. PBO; PER1000Q4W vs. PBO; At Week 12 and all other scheduled visits in Period 2	Secondary analysis is at Week 12.
		Composite	Descriptive statistics with NRI	Maintenance	No between-treatment comparison; At Week 24 and all other scheduled visits in Period 3A	Secondary analysis is at Week 24.
		Composite	Descriptive statistics with NRI	Maintenance Primary; Maintenance Secondary; Maintenance Tertiary	No between-treatment comparison; At Week 60 and all other scheduled visits in Period 3B	Secondary analysis is at Week 60.

Measure	Variable	Estimand	Analysis Method	Population	Comparison and Timepoint	Analysis Type
TJC68; SJC66; PGA VAS; PatGA VAS; Pain VAS	Change from baseline (and/or percent improvement from baseline)	Hypothetical	MMRM with no missing data imputation	mITT	PER100Q4W vs. PBO; PER400Q4W vs. PBO; PER1000Q4W vs. PBO; At Week 12 and all other scheduled visits in Period 2	Secondary analysis is at Week 12.
		Hypothetical	Descriptive statistics with LOCF	Maintenance	No between-treatment comparison; At Week 24 and all other scheduled visits in Period 3A	Secondary analysis is at Week 24.
		Hypothetical	Descriptive statistics with LOCF	Maintenance Primary; Maintenance Secondary; Maintenance Tertiary	No between-treatment comparison; At Week 60 and all other scheduled visits in Period 3B	Secondary analysis is at Week 60.
HAQ-DI	Change from baseline (and/or percent improvement from baseline)	Hypothetical	MMRM with no missing data imputation	mITT	PER100Q4W vs. PBO; PER400Q4W vs. PBO; PER1000Q4W vs. PBO; At Week 12 and all other scheduled visits in Period 2	Secondary analysis is at Week 12.

Measure	Variable	Estimand	Analysis Method	Population	Comparison and Timepoint	Analysis Type
FACIT-F	Change from baseline	Hypothetical	MMRM with no missing data imputation	mITT	PER100Q4W vs. PBO; PER400Q4W vs. PBO; PER1000Q4W vs. PBO; At Week 12 and all other scheduled visits in	Secondary analysis is at Week 12.
					Period 2	

Measure	Variable	Estimand	Analysis Method	Population	Comparison and Timepoint	Analysis Type
Duration and Severity of Morning Joint Stiffness	Change from baseline	Hypothetical	MMRM with no missing data imputation	mITT	PER100Q4W vs. PBO; PER400Q4W vs. PBO; PER1000Q4W vs. PBO; At Week 12 and all other scheduled visits in Period 2	Secondary analysis is at Week 12.

Measure	Variable	Estimand	Analysis Method	Population	Comparison and	Analysis Type
					Timepoint	
UU						
	-					

Abbreviations: BOCF = baseline observation carried forward; CDAI = Clinical Disease Activity Index; DAS28-ESR = Disease Activity Score – erythrocyte sedimentation rate; DAS28-hsCRP = Disease Activity Score – high-sensitivity C-reactive protein; ESR = erythrocyte sedimentation rate; FACIT-F = Functional Assessment of Chronic Illness Therapy-Fatigue; HAQ-DI = Health Assessment Questionnaire – Disability Index; hsCRP = high-sensitivity C-reactive protein; LDA = low disease activity; LOCF = last observation carried forward; MCID = Minimal Clinically Important Difference; mITT = modified intent-to-treat; MMRM = mixed-effect model for repeated measures; NRI = nonresponder imputation; Pain = Patient's Assessment of Arthritis Pain; PatGA = Patient's Global Assessment of Disease Activity; PBO = placebo; PER = Peresolimab; PGA = Physician's Global Assessment; Q4W = every 4 weeks; Q12W = every 12 weeks; RAMRIS = Rheumatoid Arthritis Magnetic Resonance Imaging Score; SDAI = Simplified Disease Activity Index; SJC66 = Swollen Joint Count – 66 joint counts; TJC68 = Tender Joint Count- 68 joint counts; VAS = visual analog scale.

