1.1. Objectives, Endpoints, and Estimands

Objectives	Endpoints
Primary	
To evaluate the efficacy of peresolimab compared to placebo in achieving ACR20	Proportion of participants achieving ACR20 at Week 12
Secondary	
To evaluate the effect of peresolimab compared to placebo for measures of disease activity To evaluate the effect of peresolimab compared to placebo for patient-reported outcome measures	 Proportion of participants achieving ACR50 or ACR70 at Week 12 Proportion of participants achieving LDA or remission at Week 12 for DAS28-hSCRP DAS28-ESR SDAI, and CDAI. Change from baseline at Week 12 for mean DAS28-hsCRP SDAI, and CDAI. Change from baseline at Week 12 for ACR core set values 68 tender joint count 66 swollen joint count, and Physician's Global Assessment of Disease Activity (VAS). Change from baseline at Week 12 for patient-reported ACR core set values Patient's Global Assessment of Disease Activity (VAS) Patient's Assessment of Arthritis Pain (VAS), and Patient's Assessment of Physical Function using HAQ-DI. Change from baseline at Week 12 for the duration and severity of morning joint stiffness and Functional Assessment of Chronic Illness Therapy-Fatigue (FACIT-F) scores. Change from baseline at Week 12 for SF-36 domains SF-36 Physical Component Summary, and
	o SF-36 Physical Component Summary, and
	 SF-36 Mental Component Summary.

Objectives	Endpoints
To evaluate the effect of peresolimab for measures of	Proportion of participants achieving LDA or
disease activity	remission at Weeks 24 and 60 for
	o DAS28-hsCRP
	o DAS28-ESR
	o SDAI, and
	o CDAI.
	 Proportion of participants achieving ACR20,
	ACR50, or ACR70 at Weeks 24 and 60.
	Change from baseline at Weeks 24 and 60 for
	ACR core set values
	o 68 tender joint count
	o 66 swollen joint count, and
	 Physician's Global Assessment of Disease
	Activity (VAS).
	• Change from baseline at Weeks 24 and 60 for mean
	o DAS28-hsCRP
	o SDAI, and
	o CDAI.
To characterize the pharmacokinetics of peresolimab	Observed trough drug concentration at Week 12
Exploratory	

Primary estimand

The primary clinical question of interest is:

What is the difference between peresolimab and placebo in the target patient population, in achieving a successful response at Week 12 without use of rescue or prohibited medications or discontinuing the study intervention?

The estimand is described by the following attributes:

- Population: Participants with moderately-to-severely active RA

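### SAP Table KDAF.4.1 derives the change in morning stiffness severity, a Week 12 secondary endpoint, from duration in minutes

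*SAP*

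**What the plan says.** The SAP treats duration and severity of morning joint stiffness as two endpoints. Section 1.1 lists "Change from baseline at Week 12 for the duration and severity of morning joint stiffness" among the secondary endpoints, and Section 4.4.2 gives "Severity of morning joint stiffness" its own line, apart from duration. Section 4.4.2.1.10 states that "The change from baseline of the duration and severity of morning joint stiffness at Week 12" will be compared with placebo by MMRM.

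Section 4.4 directs the reader to Table KDAF.4.1 for how each outcome is derived. For this measure the table has four variable rows: duration, change in duration, severity, and change in severity. The two change rows carry identical derivations, each opening "Calculated as: Observed duration" and subtracting "baseline duration".

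The description column of the same table separates the two measurements. Duration is in minutes for the day before the visit, with long values "truncated to 720 minutes for analysis". Severity is a single 11-point item scored from 0 to 10. For its analysis value the SAP specifies: "The worst level of joint stiffness in the last" 7 days.

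**The concern.** The derivation printed for change in severity names a different variable. Applied literally, it turns a change in points on a 0 to 10 scale into a change in minutes. One secondary endpoint would then reproduce another, and the severity scores would not enter the change analysis for which they were collected.

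The position of the error matters. Table KDAF.4.1 is the derivation specification for the efficacy outcomes, so it is what a programmer, and an independent validating programmer, would work from. If one follows the cell and the other follows the variable name, their results will not agree.

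**Working it through.** The plan states no figure to reproduce. The check sets the relevant text side by side.

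| | Duration | Severity |
|---|---|---|
| Unit | minutes | points |
| Range used in analysis | 0 to 720 | 0 to 10 |
| Reference period | day before the visit | worst in last 7 days |
| Listed as a Week 12 secondary endpoint | yes | yes, separately |
| Derivation of change in Table KDAF.4.1 | observed duration minus baseline duration | observed duration minus baseline duration |

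**Step 1: possible values.** Write D for duration and S for severity, at Week 0 and Week 12.
- Endpoint as named: S12 - S0, which lies between 0 - 10 = -10 and 10 - 0 = +10 points.
- Endpoint as printed: D12 - D0, which lies between 0 - 720 = -720 and 720 - 0 = +720 minutes.

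The two differ in unit, range and reference period, so no reading makes the printed formula a valid derivation of severity.

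**Step 2: comparison with the general rule.** Protocol Section 9.3.1 defines change from baseline as a variable's value at the visit minus that variable's own baseline. The SAP Introduction and SAP Section 4.9 both say that the protocol's analyses are unchanged. The rule gives S12 - S0 for severity. The other change rows shown in Table KDAF.4.1 (for example the global assessments, pain, HAQ-DI, hsCRP, ESR and FACIT-F) follow it. The severity row is the exception.

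**Step 3: could this come from reading the PDF?** That is unlikely. Each of the two change rows has its own complete derivation. The table line that carries the severity label also carries the words "baseline duration". The word severity appears in no derivation cell for this measure, and nothing there is blacked out.

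**Step 4: reach.** Table KDAF.4.2 plans an MMRM on change from baseline for both variables, comparing 100 mg, 400 mg and 1000 mg Q4W each with placebo. Three secondary comparisons at Week 12 therefore depend on the cell, as do the same comparisons at any other scheduled Period 2 visit. The MMRM in Section 4.1 also adjusts for baseline value. Under the literal reading it is unclear whether that would be baseline severity or baseline duration. With baseline duration the model would be an exact copy of the duration analysis.

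**Step 5: revision history.** The Version 3 changes include edits to this table (citations added, a disease abbreviation corrected). The history lists no correction to this row, although it notes that minor corrections may go unlisted. The error stands in the current text.

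**The case against.** The strongest answer is that this is a one-word copying slip with only one sensible reading. The row label says severity. A separate row defines the severity score. The description column says which severity value is to be analysed, and Section 4.4.2.1.10 names both variables. The protocol's general rule supplies the correct formula. On this view a careful programmer would derive the endpoint correctly, and it is too strong to say that the severity data would go unused. The comparison of 720 with 10 restates the two scales and does not measure bias. The stakes are also modest: stiffness severity is one of many secondary endpoints, no multiplicity adjustment is planned, and it enters neither the ACR response nor the DAS28, SDAI or CDAI formulas.

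Most of this stands as a limit on the practical harm. The intended derivation can be recovered, any effect on results depends on literal programming, and the documents do not show that it happened. It is also fair to call this an inconsistency in drafting more than a faulty calculation, and to note that the same words are correct in the duration row. None of this makes the severity row right. A reader has to override the SAP's designated derivation table to obtain a prespecified secondary endpoint.

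**Conclusion.** The concern holds. As written, Table KDAF.4.1 defines the change in stiffness severity as a change in stiffness duration. If programmed literally, every record for the endpoint would be on the wrong scale (up to 720 minutes either way instead of up to 10 points), and all three Week 12 comparisons with placebo would repeat the duration result. If programmed by intent, the results are unaffected and only the document is wrong. The documents do not show which occurred. The primary endpoint and the composite disease activity measures are not involved. The error should be corrected, but it does not threaten the trial's main conclusion.

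**What to change.** In SAP Table KDAF.4.1, change the derivation in the change-in-severity row to observed severity minus baseline severity. Leave the change-in-duration row as it is.

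The version history places Version 2 before the primary outcome database lock and Version 3 before the final lock. Someone should therefore also confirm that the Week 12 severity output used the 0 to 10 item, both for the change and for the baseline covariate. The correction should be recorded in the SAP or the clinical study report. The cost is one table cell and one output check. No new data, model or sample size is needed.
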